Tralokinumab when dosed at 300 mg every other week (Q2W) demonstrated superiority over placebo in all primary and secondary endpoints at Week 16. For the primary endpoint, an IGA 0/1 was achieved for subjects treated with tralokinumab was 15.8% for versus 7.1% for placebo in ECZTRA 1 and 22.2% versus 10.9% for ECZTRA 2. Reduction of the worst daily average of Pruritus Numeric Rating Scale (NRS) \geq 4 from baseline to Week 16 was 20.0% with tralokinumab versus 10.3% with placebo in ECZTRA 1 and by 25.0% versus 9.5% with placebo in ECZTRA 2. The overall frequency and severity of AEs over 16 weeks was comparable between tralokinumab and placebo. Of the most frequently reported AEs (\geq 5% in any treatment group), upper respiratory tract infection and conjunctivitis occurred more frequently with tralokinumab versus placebo, and dermatitis atopic and skin infection occurred more frequently with placebo (Wollenberg, 2020). Tralokinumab demonstrated in Phase 3 studies that targeting IL-13 alone in is both a safe and effective therapy; however, is the overall efficacy profile does not appear to be superior to biologic agents already on the market. When compared to the results

reported from dupilumab Phase 3 SOLO 1 and SOLO 2 induction studies, response rates for achieving IGA 0/1were as high as 38% to 36% in the dupilumab 300 mg Q2W arm, compared to 10% to 8% in subjects treated with placebo (Simpson, 2016). Although tralokinumab is anticipated to the first anti-IL-13 approved for the treatment of moderate to severe AD, there remains a need to further evaluate other biologic agents targeting IL-13 pathway, to further assess anti-IL-13's potential of achieving an optimized efficacy profile in subjects with moderate to severe AD.

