Lebrikizumab is an anti-IL-13 mAb, with a different mechanism of action (MOA) than tralokinumab, as it selectively targets IL-13 and prevents formation of the IL-13Ra1/IL-4Ra heterodimer receptor signaling complex (Ultsch, 2013). In recently published data from the Phase 2b study, lebrikizumab demonstrated efficacy across all key clinical outcome measures (eg, IGA, and EASI scores) in subjects with moderate to severe AD, particularly at the highest dose level evaluated (eg, loading doses of 500 mg at baseline and week 2, followed by 250 mg of lebrikizumab administered every other week for a total of 16 weeks). Robust efficacy was observed with lebrikizumab treatment on pruritus, with improvement in Pruritus NRS score of \geq 4 points from baseline in 70% of subjects on treatment compared with 27.3 % of subjects on placebo at Week 16. In addition, changes of at least 4 points in the Pruritus NRS score were seen as early as Day 2 in 15.3% [9 of 59] subjects treated with lebrikizumab at the highest dose level, as compared to 4.5% [2 of 44] subjects treated with placebo. These promising clinical observations associated with itch reduction in subjects treated with lebrikizumab support the preclinical evidence that IL-13 directly sensitizes sensory neurons to respond to pruritogens (Miron 2018). In addition to the enhanced efficacy profile demonstrated by the Phase 2 results, lebrikizumab was generally well tolerated, and had a favorable safety profile consistent with previous lebrikizumab studies conducted in AD and the extensive asthma Phase 2b and Phase 3 programs which enrolled over 1000 subjects (Hanania, 2016, Korenblat, 2018). Common TEAEs (> 5% in any lebrikizumab group) included upper respiratory tract infection. nasopharyngitis, headache, injection site pain, and fatigue. Serious TEAEs including peripheral edema, chronic obstructive pulmonary disease, and pulmonary embolism were reported by 2 of 52 placebo subjects (3.8%) and by 4 of 228 lebrikizumab subjects (1.8%), which include reports of chest pain, periprosthetic fracture, hernial eventration, and panic attack (Guttman-Yassky, 2020).

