- ^c For females of childbearing potential (FCBP), Urine (or serum) pregnancy test at Day 1, and urine pregnancy tests every 4 weeks thereafter are required. At each study visit, the Investigator will counsel FCBP subjects on pregnancy precautions for the duration of the study.
- ^d Further analysis on samples that are positive for ADA may be performed, including assessment of neutralizing antibodies when warranted.
- ^e An optional skin biopsy procedure will be performed to measure tissue biomarkers including target expression levels and inflammatory biomarkers in subjects who consented.
- ^f The pharmacogenetic sample will be collected from subjects, provided that necessary governmental and local approvals have been obtained. If needed, the pharmacogenetic sample can be collected at any subsequent timepoint during the study.
- ^g The vIGA-AD must be conducted before the EASI assessment.
- ^h Pruritus NRS will be collected daily in a subject ePRO during the screening period. Scores will be captured daily from Day 1 (Baseline) through Week 4, followed by subsequent administration only on study visit/study drug administration days. Score recorded at Day 1(Baseline) (pre-dose) should be used to assess eligibility criteria. The electronic patient-reported outcome handheld device should be returned at the EOT/ET Visit.
- ⁱ Once weekly IP administration (CC-93538 or placebo: subcutaneous [SC] doses on Day 1 followed by SC doses weekly from Week 1 through Week 15 [ie, a total of 16 weekly SC doses inclusive of the Day 1 dose]). The first 3 weekly SC doses will be administered in the clinic. Subjects will remain in the clinic for at least 30 minutes following dosing for observation for the first 3 visits.

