Serum antibodies CC-93538	X	X	Further analysis on samples that are positive for anti-drug-antibodies (ADA) may be performed, including assessment of neutralizing antibodies when warranted.
Serum CC-93538 pharmacokinetic (PK) sample	Х	Х	
Whole blood and serum biomarker samples	X	Х	

Table 5:Follow Up Period Procedures

Study Procedure	Follow-Up	(FU) Period	
Visit Label	Initial Follow Up Visit 18 (Week 24)	Final Follow Up/ End of Study (EOS) Visit 19 (Week 32)	Additional Notes (if applicable)
Visit Timing (Visit Window)	EOT Visit +8 Weeks (±7 day)	EOT Visit Last Dose +16 Weeks (±7 day)	All visits conducted during the Follow Up Period are onsite visits.
Skin Biopsy (Optional)		Х	An optional skin biopsy procedure will be performed to measure tissue biomarkers including target expression levels and inflammatory biomarkers in subjects who consented
validated Investigator Global Assessment of Atopic Dermatitis (vIGA-AD)	Х	Х	The vIGA-AD must be conducted before the EASI assessment. Further information on this assessment is available in Section 6.4.1 and Appendix C
Eczema Area and Severity Index (EASI)	Х	Х	Further information on this assessment is available in Section 6.4.2 and Appendix D

Table 5: Follow Up Period Procedures (Continued)

6. **PROCEDURES**

Assessments and procedures for the Screening Period (Table 3), Treatment Period (Table 4), and the Follow-up Period (Table 5) are included in Section 5 the Table of Events. Study assessments and procedures are also described in Section 6. The day of administration of the first dose of IP is defined as Day 1 (Baseline/pre-dose).

It is recommended that the study visits are scheduled in the morning. Whenever possible, the assessment order sequence, as outlined in the Table of Events Section 5, should remain constant and should be conducted at approximately the same time of day throughout the study.

Any questions regarding the protocol should be directed to the Celgene Medical Monitor or designee.

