6.1. Screening Period

Screening evaluations will be performed for all subjects to determine study eligibility. These evaluations must be completed within 28 days (4 weeks) prior to receiving the first dose of IP unless noted otherwise below. Waivers to the protocol will not be granted during the conduct of this study, under any circumstances.

Screening procedures, as specified in the Table of Events detailed in Section 5, Table 3, will be performed for all subjects to determine study eligibility. All screening procedures must be completed within 4 weeks prior to receiving the first dose of IP.

The electronic patient-reported outcome (ePRO) instrument on a handheld device will be distributed to subjects at the Screening Visit. After completion of a training module, the Pruritus NRS will be completed by the subject daily for at least the last week (7 days) during the Screening Period (prior to Day 1); however, value to assess inclusion criteria will be assessed on Day 1 (Baseline/pre-dose).

Safety laboratory analyses and all assessments will be performed. Screening laboratory values must demonstrate subject eligibility; however, analytes may be repeated (and analysed by the central laboratory) within the screening window, if necessary.

Written, signed, and dated informed consent from the subject prior to the performance of any study related procedures must be obtained by the Principal Investigator or designee (refer to Section 12.3 for further details regarding obtaining subjects informed consent). A copy of the signed informed consent must be given to the subject for his/her records.

The following evaluations will be performed at screening as specified in the Table of Events, after informed consent/assent has been obtained:

- Assessment of inclusion/exclusion criteria
- Demographics and baseline characteristics
- Medical history including atopy status (documentation of AD history, other atopic conditions, and past pharmacotherapy for AD, and other atopic conditions) and as well as details of any prior therapy or procedures to treat AD or other atopic conditions.

- Prior therapy and concomitant therapy (including all procedures occurring ≤ 28 days before screening).

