For the secondary endpoint of time to achieve at least 4 points of improvement in the severity of pruritus NRS scale in the first 16 weeks of treatment, the distribution of times to the first event of 4-point improvement will be compared based on Kaplan-Meier (K-M) and log-rank approaches. Comparisons versus placebo, for each dose group separately, will be based on a stratified log-rank test with associated p-value provided. The stratification levels are: (1) Japan region, (2) RoW region and IGA score 3, and (3) RoW region and vIGA-AD score 4. The K-M estimates for the cumulative proportions of subjects achieving a 4-point improvement, by specific timepoints, will be provided by dose group as well as differences with placebo and associated 95% confidence intervals. These will be reported at various timepoints (eg, Day 1 to 28, followed by weekly assessments). Censoring rules will be described in the SAP.

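### Should the itch-onset endpoint count its 4-point improvement from a 7-day mean rather than from the single Day 1 score?

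*Combined protocol and SAP*

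**What the plan says.** Section 9.6.2.1 defines the endpoint by its event: "the distribution of times to the first event of 4-point improvement will be compared based on Kaplan-Meier (K-M) and log-rank approaches". Each dose is compared with placebo by a stratified log-rank test with a p-value. Kaplan-Meier differences are reported over Days 1 to 28 and then weekly. No reference score is named. The onset row of Table 2 also omits it, although the rows for percent change and for 4-point response in Pruritus NRS both refer to Baseline.

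Elsewhere Baseline means Day 1. The opening of Section 6 states: "The day of administration of the first dose of IP is defined as Day 1 (Baseline/pre-dose". Note h to Table 4 says "Score recorded at Day 1(Baseline) (pre-dose) should be used to assess eligibility criteria", and Section 6.1 says the "value to assess inclusion criteria will be assessed on Day 1 (Baseline/pre-dose". Section 6.2 speaks of the baseline NRS on Day 1 and lists the NRS among the efficacy assessments.

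Daily scores also exist before Day 1. Under Section 6.1, "the Pruritus NRS will be completed by the subject daily for at least the last week (7 days) during the Screening Period". No analytic use is given for them. Each score is an integer from 0 to 10 covering the past 24 hours (Section 6.5.1). Section 9.1 refers analysis details that Section 9 does not give to the SAP. No separate SAP text is in the document supplied.

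**The concern.** One 24-hour itch score carries day-to-day error. If it is the baseline, that error enters every later comparison: 28 daily looks to Week 4 and 12 weekly looks to Week 16, 40 in all. A chance high score on Day 1 makes the event easy to reach, and a chance low score makes it hard. This happens in every arm, so false onsets and missed onsets dilute the contrast with placebo. Seven or more earlier scores, already collected, could average much of this error away at no cost to patients.

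The stake is power for the log-rank test and clarity of the early Kaplan-Meier curves. A baseline left open would also allow a choice after the data are seen, on an endpoint that carries p-values.

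**Working it through.** **1. The plan's own figure.** No power, event count or hazard ratio is stated for this endpoint. The primary power in Section 9.3 (difference 35, SD 50, 45 per arm, two-sided 0.05) reproduces: 35 / (50 × √(2/45)) = 35 / 10.54 = 3.32, and Φ(3.32 − 1.96) = 0.913 against a stated 90%.

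**2. How much error averaging removes.** Let daily error have SD σ and lag-1 correlation ρ. A single Day 1 score has error variance σ². A 7-day mean has (σ²/7) × [1 + 2 Σ (1 − k/7) ρ^k], summed over k = 1 to 6:

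- ρ = 0: 1/7 = 0.14 σ²
- ρ = 0.3: (1 + 2 × 0.341)/7 = 0.24 σ²
- ρ = 0.5: (1 + 2 × 0.717)/7 = 0.35 σ²
- ρ = 0.8: (1 + 2 × 1.742)/7 = 0.64 σ²

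The benefit therefore depends on ρ as well as on σ, and the documents give neither.

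**3. Simulated power with stable itch.** The following is assumed and is not in the documents: mean itch 7 (between-subject SD 1.5), true mean drop 3.0 versus 1.5 (SD 2), exponential onset with a 28-day constant, ρ of 0, 0.3 or 0.5, and an unstratified log-rank test. I used 45 per arm and a Day 1 score of at least 4. The drops imply 4-point rates of about 1 − Φ((4 − 3.0)/2) = 0.31 and 1 − Φ((4 − 1.5)/2) = 0.11. Section 1.3.1 quotes "25.0% versus 9.5% with placebo in ECZTRA 2". With 1,500 trials per setting the Monte Carlo SE is about 0.013.

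| Daily SD | Day 1 score | Rounded 7-day mean | Gain |
|---|---|---|---|
| 0.5 | 0.77–0.78 | 0.79–0.80 | 0.02–0.03 |
| 0.75 | 0.73–0.75 | 0.77–0.80 | 0.04–0.06 |
| 1.0 | 0.62–0.63 | 0.73–0.77 | 0.11–0.15 |
| 1.3 | 0.44–0.49 | 0.62–0.65 | 0.13–0.20 |
| 1.6 | 0.30–0.35 | 0.47–0.49 | 0.12–0.19 |

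A second model (50 per arm, 10% dropout, mean itch 7.2, reductions of 22% versus 40%) agrees in direction. At ρ = 0, power goes from 0.56 to 0.72 at SD 1.0 and from 0.29 to 0.49 at SD 1.5. Type I error was 0.037–0.056 across both models and both baselines.

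**4. Higher correlation.** At ρ = 0.8 the second model gives 0.66 to 0.66 at SD 0.5, 0.54 to 0.59 at SD 1.0, 0.31 to 0.36 at SD 1.5, and 0.21 to 0.21 at SD 2.0. Under the assumptions of step 3, with ρ = 0.8, the gain is about 0.02–0.06 for SD 0.5 to 1.6.

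**5. Drift during the week.** Steps 3 and 4 assume that itch is stable before Day 1. Topical treatments need only be stopped 7 days before Day 1 (Sections 4.3 and 8.2), and the emollient need only start 7 days before (Sections 4.2 and 8.3). The averaging window can therefore be the washout and run-in week. If itch rises linearly by D points over the window, the mean lies D/2 below the Day 1 level. With D = 2, a 4-point fall from the mean is a 5-point fall from Day 1. Rounded mean minus Day 1, in power, under the assumptions of step 3:

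| Assumed rise, ρ | SD 0.5 | 0.75 | 1.0 | 1.3 | 1.6 |
|---|---|---|---|---|---|
| none, 0.3 | +0.01 | +0.04 | +0.10 | +0.16 | +0.15 |
| 1 point, 0.3 | −0.05 | +0.02 | +0.12 | +0.20 | +0.21 |
| 2 points, 0.3 | −0.11 | −0.06 | +0.04 | +0.17 | +0.22 |
| 2 points, 0.8 | −0.12 | −0.08 | −0.04 | +0.01 | +0.09 |

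Falling itch is also possible and was not simulated.

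**6. Can the documents settle the SD?** Section 1.3.1 reports a Day 2 change of at least 4 points in another trial, "as compared to 4.5% [2 of 44] subjects treated with placebo" (exact 95% CI 0.6–15.5%). Even if that trial used a single-score baseline, which is not stated, the observed rate and its lower limit imply daily SDs from 0.6 to 2.2, depending on ρ and on any early true change. That covers everything from a negligible gain to a useful one. Effect size matters too. For the larger effect in that trial ("in 70% of subjects on treatment compared with 27.3 % of subjects on placebo at Week 16"), with stable itch and ρ = 0.3, the gains are 0.00 / 0.01 / 0.05 / 0.13 / 0.16 across the five SDs.

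**The case for a change.** The best case for changing the plan is that the omission is real and the remedy is cheap. The event definition names no reference score, and Section 9.6.2.1 defers censoring to the SAP by name but not the baseline. The stable-itch gain appears under two different sets of assumptions. Rounding keeps the 4-point bar comparable for integer scores, and the diary data already exist. Naming the baseline before unblinding is good practice whatever the SD.

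The omission stands, and so does the gain at moderate SD with low correlation and stable itch. The step to a better baseline does not. The rounded mean loses no power only on the grid in step 3, and steps 4 and 5 show nil gains and losses under conditions the protocol makes plausible. Day 1 also shares a condition with later visit-day scores that screening diary days need not share: antihistamines are withheld for 24 hours before a visit (Section 8.1). Changing the baseline for onset alone would separate it from the other two NRS endpoints, so a subject could be a Week 16 responder without ever having an onset. Averaging also leaves the error in later scores untouched. In the second model at SD 2.0, some 70–80% of placebo subjects become events under either baseline.

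**Conclusion.** No change follows. The wording gap is one that analysts fill sensibly: Day 1 pre-dose is the only defined Baseline, it serves the other NRS endpoints, and Section 9.1 already leaves such definitions to the SAP. No stated rule gives a wrong result.

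The 7-day mean is a trade-off. Its effect on power runs from a loss of about 0.12 to a gain of about 0.2, depending on daily SD, day-to-day correlation and drift in the screening week, none of which the documents give. Under either baseline type I error stays near 0.05. The endpoint is a non-key secondary outside the dose hierarchy with no power claim, and no primary or key secondary conclusion turns on the choice. This judgement rests on the assumed simulation settings above and on reading Day 1 as the intended baseline.

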	EASI-75	Proportion of subjects with at least a 75% improvement from Baseline in Eczema Area and Severity Index (EASI-75) at Week 16	Week 16
Secondary	Change in Pruritus Numerical Rating Scale (NRS)	Percent change from Baseline in Pruritus NRS at Week 16	Week 16
	Pruritus NRS Response Threshold	Proportion of subjects with Pruritus NRS change of \geq 4 points from Baseline at Week 16	Week 16
	Onset of Change in Pruritus NRS	Time to achieve at least 4 points of improvement in the severity of pruritus NRS scale in the first 16 weeks of treatment	All planned time points through Week 16
	EASI-90	Proportion of subjects with at least a 90% improvement from Baseline in Eczema Area and Severity Index (EASI-90) at Week 16	Week 16
	SCORing Atopic Dermatitis (SCORAD) Index	Mean change in SCORAD Scores from Baseline at Week 16	Week 16
	AD Body Surface Area (BSA) involvement	Percent change in BSA involved with AD from baseline at Week 16	Week 16
	Safety and Tolerability	Safety and tolerability evaluated by the incidence, severity, and relationship to CC-93538 of adverse events (AEs), serious adverse events (SAEs), clinical laboratory abnormalities, as well as an evaluation of the presence of serum antibodies to CC-93538.	All planned time points through Final Follow Up Visit
	Pharmacokinetics (PK)	Serum trough concentration of CC- 93538	All planned time points through Final Follow Up Visit

Table 2:Study Endpoints

Endpoint	Name	Description	Timeframe
Exploratory	Onset of Action for Key Efficacy Parameters	Proportion of subjects with at least a 50% improvement from Baseline in Eczema Area and Severity Index (EASI-50) in the first 4 weeks of treatment	All planned time points through Week 4
		Proportion of subjects to achieve EASI-75 in the first 4 weeks of treatment	All planned time points through Week 4
		Proportion of subjects with an vIGA- AD score of 0 (clear) or 1 (almost clear) in the first 4 weeks of treatment	All planned time points through Week 4
	vIGA-AD 0 or 1 and EASI-75	Proportion of subjects achieving both a vIGA-AD score of 0 (clear) or 1 (almost clear) and an EASI-75 at Week 16	Week 16
	PROMIS [®] Sleep Disturbance Short Form 8a	Mean change in sleep disturbance total score from Baseline to Week 16	Week 16
	Patient Oriented Eczema Measure (POEM) Score	Mean change in POEM scores from Baseline to Week 16	Week 16
	Dermatology Quality of Life Index (DLQI) Score	Mean change in DLQI score from Baseline to Week 16	Week 16

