6.5.1. Pruritus Numeric Rating Scale

Pruritus will be assessed by the subject using the Pruritus NRS, which was developed and validated as a single item, patient reported outcome (PRO) of itch severity. Clinical response is indicated by $a \ge 2$ to 4-point change from baseline in Peak Pruritus NRS score (Yosipovitch, 2019) The intensity of pruritus will be assessed based on last 24 hours using a validated 11-point NRS, ranging from 0 ("no pruritus") to 10 ("the worst pruritus imaginable"). The subject will complete an electronic diary recording the intensity of their pruritus on daily basis, through Week 4, and weekly (eg, on study visit/study drug administration days) thereafter through the Week 16 visit.

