9.6.2. Efficacy Analysis of Secondary Endpoints

9.6.2.1. Analysis Methods

For the first key secondary endpoint of proportion of subjects with both a vIGA-AD score of 0 (clear) or 1 (almost clear) and a reduction of 2 or more points in vIGA-AD score from Baseline at Week 16 will be analyzed based on the mITT population using a stratified Cochran-Mantel-CMH test at a two-sided 5% significance level. The randomization stratification levels are: (1) Japan region, (2) RoW region and vIGA-AD score 3, and (3) RoW region and vIGA-AD score 4. Estimates of the differences in proportions between each treatment group versus placebo, and associated 95% confidence intervals will be provided along with p-values. Missing endpoint values (eg, due to study dropout or other reasons for lack of assessment) will be imputed as non-responders. A sensitivity analysis will be conducted based on defining subjects who initiate rescue therapy (prior to Week 16) as missing and treated as non-responders.

The second key secondary endpoint of proportion of subjects with at least a 75% improvement from baseline in Eczema Area and Severity Index (EASI-75) at Week 16 will be analyzed in the same manner as above.

The hierarchical testing approach used for the primary endpoint will be utilized to adjust for multiplicity with respect to the 3 active doses for each of these key secondary endpoints. However, multiplicity adjustments are not implemented across the primary and 2 key secondary endpoints simultaneously.

The following endpoints will be analyzed in the same manner as the key secondary endpoints, excepting that p-values will not be provided:

- The secondary endpoint of proportion of subjects with Pruritus NRS change of ≥ 4 from Baseline at Week 16
- The secondary endpoint of proportion of subjects with a 90% improvement from Baseline in EASI (EASI-90) at Week 16

The following endpoints will be analyzed in the same manner as the primary endpoint, excepting that p-values will not be provided:

- The secondary endpoint of percentage change from baseline in Pruritus NRS at Week 16
- The secondary endpoint of percent change in SCORAD Scores from Baseline at Week 16

• The secondary endpoint of mean percent change in Body Surface Area (BSA) involved with AD from Baseline at Week 16

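### Does time to first 4-point itch improvement need a confirmation rule, given that any one of 40 single-day scores can trigger the event?

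*Combined protocol and SAP*

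**What the plan says.** Table 2 (Section 2) lists, as a secondary endpoint on the onset of change in itch: "Time to achieve at least 4 points of improvement in the severity of pruritus NRS scale in the first 16 weeks of treatment". Section 9.6.2.1 makes the event the first such improvement: "the distribution of times to the first event of 4-point improvement will be compared based on Kaplan-Meier (K-M) and log-rank approaches". It adds that each dose's comparison with placebo "will be based on a stratified log-rank test with associated p-value provided". For the other non-key secondary efficacy endpoints (Week 16 itch, EASI-90, SCORAD, BSA) the same section copies the key secondary or primary methods, "excepting that p-values will not be provided".

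On measurement, Section 6.5.1 says: "The intensity of pruritus will be assessed based on last 24 hours using a validated 11-point NRS". Footnote h to Table 4 gives the schedule: "Scores will be captured daily from Day 1 (Baseline) through Week 4, followed by subsequent administration only on study visit/study drug administration days".

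No confirmation, averaging or persistence rule is stated for this endpoint. Section 9.6.2.1 adds "Censoring rules will be described in the SAP", and Section 9.1 leaves other analysis details to the SAP as well. The public document contains no separate SAP text.

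**The concern.** A first-event rule over many looks collects chance events; a comparison at one fixed visit does not. If itch varies from day to day, some subjects with no lasting change will record one score 4 points below baseline. Such events raise the Kaplan-Meier curve in every arm, placebo included. Most of them would fall in the daily window up to Week 4, where an onset claim is read. They can also blur the contrast between arms.

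The endpoint draws attention because it is the only non-key secondary efficacy endpoint reported with a p-value. The itch baseline for analysis is not named outright either, although at least 7 daily scores are collected before Day 1. A sensitivity analysis that requires two consecutive qualifying scores seems a cheap safeguard.

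**Working it through.** **Plan's own figures.** The plan gives no power, event rate or SD for this endpoint. Its primary power can be reproduced: with 45 per group, difference 35 and SD 50, Φ(35 / (50 × √(2/45)) − 1.96) = Φ(3.32 − 1.96) = 91.3%, against about 90% stated. Also 45 / 0.9 = 50 per arm, as planned.

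**Number of looks.** Days 2 to 29 give 28 daily scores and Weeks 5 to 16 give 12 weekly scores: 28 + 12 = 40. Ending daily scoring at Day 28 and counting visits from Week 4 gives 27 + 13 = 40.

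**Simple bound.** If each score independently has a chance p of a false 4-point drop, P(at least one in 40) = 1 − (1 − p)^40. For p = 0.5%, 1% and 2% this is 18%, 33% and 55%. Section 1.3.1 gives one possible anchor from another trial at Day 2: "as compared to 4.5% [2 of 44] subjects treated with placebo". With p = 2/44 the formula gives 84%. That overstates the problem, because all 40 comparisons share one baseline score and are not independent. In simulation at SD 1.5 with independent errors, the Day 2 rate is also about 4.5%, yet the 40-score rate is 44%. The anchor is weak in any case: its exact 95% CI is 0.6–15.5%, and some of those changes may be real.

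**Simulation.** All inputs except the schedule and the entry cut-off are assumptions:

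- true level N(7, SD 1.5); scores rounded and limited to 0–10; Day 1 score at least 4;
- for power, 50 per arm, mean improvement 1.5 vs 3.0 (individual SD 1.5), exponential onset with a 28-day time constant, unstratified log-rank test at two-sided 0.05.

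Ranges run over independent errors and a lag-1 correlation of 0.5.

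| Assumed day-to-day SD | No true change, event by Week 16: first score | Same: two consecutive | Power: first score | Power: two consecutive |
|---|---|---|---|---|
| 0.5 | 0% | 0% | 95% | 91–92% |
| 0.75 | 1–2% | 0.1–0.2% | 92% | 88–89% |
| 1.0 | 10–12% | 1–3% | 81–82% | 81–84% |
| 1.5 | 41–44% | 11–17% | 45–49% | 57–65% |
| 2.0 | 66–68% | 27–36% | 22–26% | 36–45% |

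At SD 1.5, 34–39 of the 41–44 points arise by Day 29. Type I error is 4.2–5.8% under the planned rule and 4.0–5.7% under the two-score rule.

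**Does power depend on onset speed?** Yes. With a 56-day time constant and SD 0.75, power is 85–86% under the planned rule and 76–77% under the two-score rule, a loss of 8 to 10 points rather than the 3 to 4 in the table. At SD 1.0 it is 69–73% against 69%.

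**Would the gap between the two rules measure noise?** No. At SD 0.75, about 62% of the active arm have an event under the planned rule and 44% under the two-score rule, a gap of 62 − 44 = 18 points. Pure chance events are only about 1.5%. About 85% of the active subjects in the gap truly improve by at least 2 points, so most are partial improvers near the threshold. In the other direction, at SD 1.5 the two-score rule still counts 11–17% of subjects with no change, because error in the Day 1 score remains.

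**Would a 7-day mean baseline help?** Not reliably. At SD 1.5, chance events are 20–23% if itch is stable in that week, 3–6% if it rises 2 points and 54–58% if it falls 2 points, against 41–44% as planned. With a 2-point rise at SD 0.75, power is 76% against 92%. That week overlaps the topical washout (Section 4.3) and the emollient run-in (Section 4.2), so drift is plausible.

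**The case for a change.** The best case for a change is that the check costs only SAP wording and programming, needs no new data, and would leave the planned analysis and its p-value as they are. Because the SD is unknown, the trial's own data would show whether confirmation matters, and a check added after unblinding would look data-driven. The p-value also gives this endpoint more weight than its neighbours.

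Some of this stands. The count of 40, the missing confirmation rule and the isolated p-value are all correct. If the SD is about 1.5 or more, the curves carry many chance events and the two-score rule has more power. A trial team could reasonably add the check as an option.

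It does not amount to a needed correction, because the result could not be read in the way intended: the gap mixes noise with partial and short-lived true improvement. The rule also has costs. Among simulated subjects with a true improvement of at least 4 points, it counts 88–92% instead of 98%, and the median event day moves from 13–25 to 22–36. After Week 4 it asks for persistence over a week, and a first qualifying score at Week 16 cannot be confirmed.

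On the baseline, footnote h to Table 4 and Sections 6 and 6.1 all label Day 1 pre-dose as Baseline. An analyst would use the Day 1 score; naming it in the SAP is ordinary detail.

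**Conclusion.** No change follows. Time to first attainment is a fair reading of an endpoint about onset, and sensitivity to single good days is the price of detecting onset early. The comparison between blinded randomized arms stays valid. The size of the effect depends on a within-subject SD that the documents do not give: chance events are 1–2% or fewer at SD 0.75 or below, 10–12% at 1.0, and 41–44% at 1.5. The two-score rule helps power at SD 1.5 and above, is roughly neutral at 1.0, and costs about 3 to 10 points at 0.75 depending on onset speed.

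Readers should take the Kaplan-Meier proportions as ever having reached a 4-point improvement, not as sustained response, and judge them against the placebo curve. The two Week 16 itch endpoints, each read at one visit, avoid the repeated looks. Nothing here touches the primary endpoint, the key secondary endpoints or the testing hierarchy.
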